5 STUDY MEDICATION (STUDY DEVICE OR OTHER STUDY INTERVENTION)

5.1 Description

There is no study medication or device that is being evaluated in this study. Rather, the reminder, feedback, and incentive intervention described above will be the subject of investigation. In order to capture ICS medication use, we will use an electronic sensor device (described below) that attaches to the exterior of the ICS inhaler and transmits pressure-activated device actuation data via Bluetooth to a mobile phone app. The Propeller sensors (Propeller, Madison, Wisconsin) are FDA 510k cleared, portable device attaches onto a patient's asthma medication (see exclusion criteria in section 3.4.2 for a list of medications that are not compatible with the Propeller sensor). These devices record the time and date of each inhaler actuation and transmit this information via Bluetooth to either a smartphone or hub. Data is then sent via the cellular network to the secure Propeller server. The data will then be transmitted onto the secure, password-protected Way to Health platform through the integrated API.

6 SAFETY MANAGEMENT

6.1 Clinical Adverse Events

Clinical adverse events (AEs) will be monitored throughout the study. However, since this is a minimal risk study, we do not expect clinical adverse events to be related to study procedures.

6.2 Adverse Event Reporting

Since the study procedures are not greater than minimal risk, SAEs are not expected. If any unanticipated problems related to the research involving risks to subjects or others happen during the course of this study (including SAEs) they will be reported to the IRB in accordance with CHOP IRB SOP 408: Unanticipated Problems Involving Risks to Subjects. SAE and AE reporting are summarized in the DSMP in Appendix 2.

7 STUDY ADMINISTRATION

7.1 Treatment Assignment Methods

7.1.1 Randomization

At the time of enrollment, patients will be assigned to one of three arms using a 2:1:2 block randomization scheme with a block size of 50. Randomization will be accomplished automatically by the Way to Health web-based platform. During the Run-in interval of the study, every caregiver-child dyad will receive electronic ICS use monitoring. Participants for whom we received any adherence monitoring data and at least one text message reply by the end of week 2 will be randomized into one of three experimental conditions at the end of the Run-in period.

Participants will be randomized using block randomization, so arms 1 and 3 will have approximately equal sample sizes and arm 2 will have approximately half the number of

participants(as the study is powered to detect a difference between arms 1 and 3). A total n of 125 will be randomized, with a recruitment goal of about 50 in arms 1 and 3 and 25 in arm 2.

[figure not shown]
7.1.2 Blinding

Only the PI ([name]) and the statistics team will remain blinded to the assignment of study arm. Neither the subjects nor the study team will be blinded to the study conditions, given that the intervention groups will be receiving incentives and/or reminders (whereas the control group will not) and the study team will provide monthly incentive payments and help facilitate tech support based on the study arm.

7.2 Data Collection and Management

Each study subject will be assigned a study ID at the time of enrollment, which will serve as the means of protecting personal health information during data transfers and storage. These master study IDs will be kept in a separate CHOP network folder from the datasets and will be retained for at least 6 years according to CHOP policy A-3-9.

Epic medical record and study questionnaire data will be entered directly into the Way to Health platform (in the case of patient identifiable information) or on a paper form during the study visits. Coded electronic adherence data will be transferred electronically from the Propeller Health Platform to the Way to Health Platform via the API of the Propeller sensor. An additional data transfer will be used to extract a coded analytic data set to the secure CHOP research server for analysis. All databases created will be password-protected and only study team members will have access. All data sets downloaded through the Propeller Health or Way to Health platforms will be password-protected and stored on the CHOP secured network drive, only accessible to study team members. For a summary of data entry and transfer, refer to Figure 4 below.

Way to Health Platform:

Research material will be obtained from participant surveys entered directly into the Way to Health portal, and from the data transmitted from Propeller Health's device trackers to the WTH platform via the integrated API. Research material that is obtained will be used for research purposes only. The same procedure used for the analysis of automated data sources to ensure protection of patient information will be used for the survey data, in that patient identifiers will be used only for linkage purposes or to contact patients. The study identification number, and not other identifying information, will be used on all data collection instruments. All study staff will be reminded to appreciate the confidential nature of the data collected and contained in these databases. The Penn Medicine Academic Computing Services (PMACS) will be the hub for the hardware and database infrastructure that will support the project and is where the Way to Health web portal is based. The PMACS is a joint effort of the University of Pennsylvania's Abramson Cancer Center, the Cardiovascular Institute, the Department of Pathology, and the Leonard Davis Institute. The PMACS provides a secure computing environment for a large volume of highly sensitive data, including clinical, genetic, socioeconomic, and financial information. Among the IT projects currently managed by PMACS are: (1) the capture and organization of complex, longitudinal clinical data via web and clinical applications portals from cancer patients enrolled in clinical trials; (2) the integration of genetic array databases and clinical data obtained from patients with cardiovascular disease; (3) computational biology and cytometry database management and analyses; (4) economic and health policy research using Medicare claims from over 40 million Medicare beneficiaries. PMACS requires all users of data or applications on PMACS servers to complete a PMACS-hosted cybersecurity awareness course annually, which stresses federal data security policies under data use agreements with the university. The curriculum includes Health Insurance Portability and Accountability Act (HIPAA) training and covers secure data transfer, passwords, computer security habits and knowledge of what constitutes misuse or inappropriate use of the server. We will implement multiple, redundant protective measures to guarantee the privacy and security of the participant data. All investigators and research staff with direct access to the identifiable data will be required to undergo annual responsible conduct of research, cybersecurity, and HIPAA certification in accordance with University of Pennsylvania regulations. All data for this project will be stored on the secure/firewalled servers of the PMACS Data Center, in data files that will be protected by multiple password layers. These data servers are maintained in a guarded facility behind several locked doors, with very limited physical access rights. They are also cyber-protected by extensive firewalls and multiple layers of communication encryption. Electronic access rights are carefully controlled by University of Pennsylvania system managers. We will use highly secure methods of data encryption for all transactions involving participants' financial information using a level of security comparable to what is used in commercial financial transactions. We believe this multi-layer system of data security, identical to the system protecting the University of Pennsylvania Health Systems medical records, greatly minimizes the risk of loss of privacy. In addition, risk of loss of confidentiality will be minimized by immediately destroying paper copies of surveys after entering data into the WTH platform. Each subject will be assigned a unique identifier without identifying information, and data will be entered into an electronic database using only the unique identifier. Only trained study staff will have access to the code that links the unique identifier to the subject's identity. Electronic data will be stored on secure, password-protected firewalled servers at the University of Pennsylvania and Children's Hospital of Philadelphia.

WTH uses a role-based access control (RBAC) approach to assure that participant confidentiality and study integrity is preserved. Principle investigators and statisticians are

restricted using RBAC, with a role that provides them access to coded data sets only. Other staff such as project managers and research coordinators require access to identifiable data in order to conduct normal study operations such as follow up study visits, monitoring enrollment statuses, and updating contact information. These roles can toggle between identified and coded views as needed. Prior to receiving access to the platform, the study's project manager must confirm that the staff person has been added to the IRB and has completed their CITI Protection of Human Subjects Research Training – ORA. Research staff users must read and sign the WTH Data Security Agreement upon initial login to the platform. They cannot access PHI or any other data on the platform until that agreement has been reviewed and signed.

The WTH Team supports all research studies run on the platform. Default views within the platform for all WTH staff display coded participant data. As a part of support and troubleshooting, the WTH Team is trained to use only these coded views. In rare cases where the issue involves viewing identifiable participant data, the WTH team may need to view this data to assist the study team.

The WTH Team are employees of the University of Pennsylvania and Penn Medicine. All WTH team members have completed HIPAA Security training and CITI Protection of Human Subjects Research Training - ORA.

Access to the backend database is restricted and only available to a select group of developers. The database is accessible only via a secure VPN (Virtual Private Network) and cannot be accessed from the public internet at all, i.e. authorized users can only access the databases from within Penn's network and over a secure VPN channel.

To maximize security, WTH assumes that **all** data in the system is electronic protected health information (ePHI). All data at-rest is stored on encrypted disks using encryption keys managed by WTH. Encrypted disks use AES encryption with a minimum of 256-bit keys, or keys and ciphers of equivalent or higher cryptographic strength. User passwords are never stored in clear text; they are “salted” and “hashed” to eliminate data leakage. All data transmission is encrypted end to end using encryption keys managed by WTH. Transmission encryption keys use a minimum of 2048-bit RSA keys, or keys and ciphers of equivalent or higher cryptographic strength (e.g., 256-bit AES session keys in the case of IPsec encryption). Data downloads are generally prohibited by policy. Where appropriate, most datasets are blinded of all personally identifiable information when exported for analysis. A limited number of exports including identifiers exist to assist research staff with recruitment tracking and study management efforts. These datasets are only accessible to certain user roles. These user roles are required to sign and adhere to a WTH Security Agreement as described above

To monitor ongoing usage of the system and identify unauthorized usage of the system, all access to the application and the database are logged automatically. These logs are reviewed as described in the WTH policies.

WTH has automated procedures to create and maintain retrievable exact copies of ePHI utilizing our Backup Service. These backup procedures are run on a daily basis and stored in a different location. Backups are encrypted. Backups are retained for a rolling 14 day period. Recovery from backups is also tested on a quarterly basis.

Security is a paramount concern at WTH. We perform regular (at least monthly) vulnerability scans of our systems to identify and patch any known vulnerabilities in our systems. We also run Intrusion Detection Systems (IDS) to identify unauthorized system access.

1) Questionnaire Data:

This study will use *Way to Health*'s online survey tool to collect answers to survey questions from participants. Survey answers will be entered by the study team member and are stored on the *Way to Health* platform. Study staff members review the survey content to ensure that no questions in any of the surveys ask for patient identifiers. If there are problems connecting to the internet for questions to be completed on a laptop computer, a paper form of the WTH surveys will be used. All paper surveys will be recorded in WTH at the earliest possible convenience by study staff. Paper forms will be inserted into a locked box for materials to be shredded once information is entered and confirmed into WTH.

2) Electronic Adherence Data (Propeller Health sensor and platform):

Following activation of the electronic monitoring device, time-stamped data is transferred from the electronic monitoring device via Bluetooth to a smartphone or cellular modem, which then sends it via the cellular network to the Propeller platform. The cellular upload identifies the patient only by a unique identifier. The cellular transmission has no patient-identifying information and no IP addresses are collected during this information transfer. The coded daily adherence data will then be available to the study team on the secure, password-protected Propeller provider platform.

Data collected in Propeller are stored within a US HIPAA compliant system, meaning that personal health information is protected during capture, during transmission to the server, and when on the server. Propeller has been certified to offer industry leading policies and controls for data protection under the HITRUST framework. For more information, anyone (including patients and providers) can visit <https://www.propellerhealth.com/privacy-policy/>

Propeller HIPAA Adherence statement:

Data collected in Propeller are stored within a US HIPAA compliant system, meaning that personal health information is protected during capture, during transmission to the server, and when on the server. Propeller has been certified to offer industry leading policies and controls for data protection under the HITRUST framework. For more information, anyone (including patients and providers) can visit <https://www.propellerhealth.com/privacy-policy/>

3) Epic Medical Record Data:

Study staff will extract asthma-related primary care, ED, and hospital data points (see Section 4.11.1 for specific data points to be extracted) from Epic into Way to Health via individual chart review. Individual patient data will be labeled with the patient's study ID upon population of Way to Health for subsequent storage and data analysis.

4) Semi-structured interviews:

Semi-structured interviews will be recorded via two-way microphones. Recordings will be uploaded to a secure site for transcription (by ADA transcription service; agreement in place for this study). Then transcripts will be downloaded to our secure CHOP network drive and uploaded into NVivo, a qualitative software program that meets CHOP's IT standards for security, for coding and analysis.

Data Transfer Description

- 1.) Propeller platform to Way to Health platform: coded study adherence data will be transferred from Propeller Health to the Way to Health platform through the integrated API. This file will contain no PHI, only the subjects' study ID. Way to Health will use the adherence data to automatically tabulate financial incentives and send weekly adherence feedback messages to participants.
- 2.) Way to Health to CHOP Server: Coded data from the study visits, including initial survey, follow-up surveys, and electronic adherence data will be converted to a CSV file and uploaded onto the CHOP server to a dedicated research folder on the study PI's virtual desktop. No PHI will be involved in this transfer, only the subject's study ID.

The Health Analytics Unit (HAU) will assist the study staff in converting these coded data from the CSV file to an analytic file for subsequent cleaning and analysis. All transferred and created files will be stored in a password-protected folder available only to study staff on CHOP's secured shared network drive. The study key will be stored in a separate password protected folder assigned to this study. All identifiers will be deleted following publication of the study results.

Study Recruitment Tracking File:

Recruitment and enrollment tracking will be stored in a REDCap database, only available to study team members. This database will include patient identifying information necessary for registration, enrollment, and follow-up (see 9.6, waiver of HIPAA authorization). Following enrollment, this database will be used to maintain a log of enrolled patients. For families who are not enrolled, patient identifying information will be destroyed. A non-identifiable list of patients that were not enrolled will be retained for the purpose of calculating response rate.

Consent Forms:

Consent will be obtained using a physical copy of the form if enrollment is conducted in person. REDCap electronic consent will be obtained if initial enrollment is conducted via telephone. Families will receive an electronic copy of the consent form that they will digitally sign. If consent is not obtained electronically, paper consent forms will be stored in a locked filing cabinet and retained per CHOP policy A-3-9.

Anonymization:

Data will be extracted from the secure WTH platform for the purpose of data analysis. Any datasets and computer files that leave the WTH firewall will be stripped of all identifiers and individuals will be referred to by their study ID. The study ID will also be used on all analytical files.

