3.1.4 Follow-up Phase

After completion of the *Observation* interval, participants will enter into a follow-up phase. Participants will complete a brief final study survey at during months 12-13 with study staff. The study team will also assess the number of ED visits, hospitalizations, and oral steroid courses for asthma at CHOP over this time period within the CHOP EMR. Electronic monitoring of daily ICS medications will continue during the follow-up phase to assess for ongoing feasibility and acceptability of electronic monitoring, if the data is available.

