4.11 Screening and Monitoring Evaluations and Measurements

4.11.1 Medical Record Review

Variables to be abstracted from the medical chart:

- Child sex
- Date of birth
- Weight and height
- Date of qualifying hospital admission and discharge
- Asthma severity
- Last spirometry result and date of assessment (if reported)
- Name and dose of current asthma medications (both controllers and rescue)
- Number of prescriptions and refills in the prior year for each asthma medication
- Number and date of ED visits, hospitalizations, and oral steroid courses for asthma in the preceding year
- Number and date of ED visits, hospitalizations, and oral steroid courses for asthma during the 13-month study period

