4.15 Secondary Endpoints

Secondary endpoints will include the following:

- Adherence to ICS regimen in *Observation* interval (months 4-6)
- Adherence trajectory, as determined by group-based modeling of adherence patterns.
- Change in cACT score from first study visit to the second, third, fourth, and fifth study visits.
- Number of asthma-related emergency room visits, hospitalizations, and oral steroid courses between study conditions.
- Healthcare costs associated with emergency room visits, hospitalizations, and oral steroid courses between study conditions.
- Continued use of sensors in 7-13 month follow-up period (feasibility outcome)

Health system use outcomes will be assessed primarily using CHOP electronic health record data and, secondarily, via caregiver report to account for utilization that may have occurred outside of CHOP. ED visits, hospitalizations, and oral steroids courses will be characterized as asthma-specific using existing, validated asthma registry definitions that include asthma visit diagnoses, medication orders, and asthma pathway order set activation. Costs will be estimated using average insurance payments for asthma ED visits, hospitalizations, and oral steroid courses in addition to the costs of the intervention components (i.e. sensors, incentive value, and research staff support).

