7.4 Regulatory and Ethical Considerations

7.4.1 Data and Safety Monitoring Plan

Please see Appendix 2 for the DSMP for this study. A local DSMB has been appointed for this study with guidance from the Clinical Trials Office at the NHLBI. The PI has developed a number of additional strategies to ensure the accuracy, security, and validity of the various data sources. First, identifiable information will be converted to study ID for storage and analysis. Data extracted from the Epic medical record by the research assistant and the study questionnaire responses will be entered into and stored in the WTH platform at Penn by study ID. Coded adherence data from the Propeller platform will be downloaded to the WTH platform in data downloads through the API.

Second, the data sources that will contain identifiable information, namely the Propeller and WTH platforms, will be held to the highest of security standards. Please see section 7.2 for the security features of the Propeller and WTH platforms.

Please see section 7.2 for further details of the measures in place to protect data confidentiality, especially with respect to data transfers.

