Appendix 2: Data Safety and Monitoring Plan

Study Oversight:

This study will utilize an institutionally-appointed Data Safety and Monitoring Board (DSMB), which will hold DSMB yearly meetings via teleconference. The DSMB will be responsible for monitoring any data and/or safety issues and also providing recommendations as needed for the following:

- Participant safety
- Initial approval of the protocol and consent forms and subsequent amendments for human subject safety and research ethics
- Data and statistical analysis plan
- Efficacy of the study intervention
- Benefit/risk ratio of procedures and participant burden
- Selection, recruitment, and retention of participants
- Adherence to protocol requirements
- Completeness, quality, and analysis of measurements
- Notification of and referral for abnormal findings

Study Monitoring:

The data to be presented to the DSMB for review will be proposed at the first DSMB meeting and then provided in aggregate at subsequent meetings. At a minimum, recruitment and retention data, baseline characteristics, changes to the protocol and consent or planned analysis, and the following outcome data will be included: asthma medication adherence and asthma-related healthcare utilization. In addition, data quality (timeliness and completeness of data collection, resolution of discrepancies), safety data (adverse events (AEs), serious adverse events (SAEs), and unanticipated problems), and study conduct (protocol deviations) will also be included.

Ongoing monitoring of recruitment will be tracked using a master screening log stored on the study's Way to Health database at the University of Pennsylvania. Way to Health is an NIH-sponsored, web-based platform that automates many of the research functions necessary for conducting randomized controlled trials of behavioral incentives.

Monitoring of data collection will be performed by the research project manager and research assistant:

- Monthly review of adherence data from Way to Health
- Monthly review of EHR data on asthma-related ED visits and hospitalizations

Missing data will be managed by running twice monthly data query reports in the Way to Health database. Data discrepancies will be resolved by the study research assistant and other study staff with corrections and/or comments entered into the Way to Health database within one week of receiving data query.

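### Cheap improvement: in-study asthma events are extracted by chart review by a study team not blinded to arm, although the plan already names definitions that could be applied as a fixed rule without the arm

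*Combined protocol and SAP*

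**What the plan says.** - **How events are captured.** Section 7.2 has study staff move asthma-related items "from Epic into Way to Health via individual chart review" and refers to 4.11.1 for the list. The last item there is "Number and date of ED visits, hospitalizations, and oral steroid courses for asthma during the 13-month study period".
- **Who does it.** Section 3.1.4: "The study team will also assess the number of ED visits, hospitalizations, and oral steroid courses for asthma at CHOP". Section 7.4.1 refers to "Data extracted from the Epic medical record by the research assistant". Appendix 2 states "Monitoring of data collection will be performed by the research project manager and research assistant" and lists among the tasks "Monthly review of EHR data on asthma-related ED visits and hospitalizations".
- **Who is blinded.** Section 7.1.2 keeps only the PI and the statistics team masked. It adds: "Neither the subjects nor the study team will be blinded to the study conditions". The reasons given are that the conditions are visible and that staff make payments and give technical support according to arm.
- **How an event is classed.** Section 4.15 says ED visits, hospitalizations and steroid courses are classed as asthma-specific "using existing, validated asthma registry definitions that include asthma visit diagnoses, medication orders, and asthma pathway order set activation". CHOP records are the main source, and caregiver report is the second source for care elsewhere.
- **What the events feed.** They feed the event counts and costs in 4.15, and the time-to-event, recurrent-event and cost-offset analyses in 4.18. Section 4.17 says the trial is not powered for health outcomes or cost offset, but that effect sizes on utilization are to help power a later multicenter study.

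**The concern.** Events are collected by reading charts one at a time, and the plan describes the team that reads them as knowing the arm. No section masks the abstractor or provides for duplicate abstraction or blinded adjudication. Section 4.15 supplies criteria built from structured record elements, but the plan does not say whether a program runs them or a person applies them while reading.

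Hypothesis 1.2 in 4.18 states the expected ordering: later and fewer events, and lower costs, in Arm 1. Where a contact is ambiguous, an abstractor who knows both the arm and the hypothesis could search or classify unevenly. An error of that kind is systematic. Masking the statisticians does not remove it, and it would pass into the effect sizes meant for planning the next trial.

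**Working it through.** **Step 1. The passages side by side.** Section 7.2 describes extraction; 4.15 describes classification. They are compatible, because an abstractor could extract by hand and apply the registry criteria while doing so. The gap is that neither section requires the criteria to be applied as a fixed rule or without the arm. Knowledge of arm follows from the general statement in 7.1.2; no sentence addresses the abstractor specifically.

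**Step 2. Where judgement can enter.** Dated ED visits and admissions at one institution are fairly objective. Judgement enters mainly in whether a contact was for asthma and whether a steroid course counts. Steroid courses enter the counts and the 4.15 costs. They do not enter the time-to-event analysis in 4.18, which uses ED and inpatient visits only.

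**Step 3. The plan's own sample size (4.17).** Inputs: 65% versus 35%, two-sided 0.05, 80% power, about 20% loss.

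n = (1.960 + 0.842)² × (2 × 0.65 × 0.35) / 0.30² = 39.7, so 40 per arm; 40 / 0.80 = 50 enrolled.

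The plan's figures are reproduced. The point does not depend on them; they only supply arm sizes for the illustration.

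**Step 4. Illustration of size.** The capture shortfalls are assumptions, since the documents give none. Take no true effect, and let Arm 1 capture be a fraction c of Arm 3 capture. The apparent rate ratio is then 1 × c: 0.95 for a 5% shortfall and 0.90 for a 10% shortfall, whatever the event rate.

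For the false-positive rate, use the roughly 50% with an ED visit or inpatient stay within 6 months (4.17) as the true proportion in both arms, and assume the shortfall applies to that proportion. With p₁ = 0.50c, p₃ = 0.50 and a two-sided two-proportion test:

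| Shortfall in Arm 1 | p₁ vs p₃ | False-positive rate, 50 per arm | 40 per arm |
|---|---|---|---|
| none | 0.500 vs 0.500 | 5.0% | 5.0% |
| 5% | 0.475 vs 0.500 | 5.7% | 5.6% |
| 10% | 0.450 vs 0.500 | 7.9% | 7.3% |

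At 50 per arm, a 10% shortfall is 50 × (0.50 − 0.45) = 2.5 children out of 25 with an event.

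**Step 5. Comparison with sampling error.** A constant hazard giving 50% in 6 months is −ln(0.5) / 0.5 = 1.39 events per child-year. An assumed upper value of 2.0 allows for repeat events. With 40 children followed for one year, that is 40 × 1.39 = 56 to 40 × 2.0 = 80 events per arm, and 5-10% of these is about 3 to 8 events. The Poisson 95% interval around a rate ratio of 1 is exp(±1.96 × √(2/E)):

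- E = 56: exp(±0.370) = 0.69 to 1.45
- E = 80: exp(±0.310) = 0.73 to 1.36

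An apparent ratio of 0.90-0.95 lies well inside both.

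**Limit of these inputs.** The 50% figure refers to children with at least two prior hospitalizations, whereas inclusion criterion 4 also counts ED visits and outpatient visits with steroid courses. The true event rate may therefore differ.

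**The case against.** The strongest reply is that the main safeguard is already written. Section 4.15 fixes validated criteria, 7.2 can be read as manual extraction under those criteria, and the monthly review in Appendix 2 is the same for every arm. The endpoints are secondary and openly unpowered, the primary endpoint comes from sensors, and any plausible distortion is small beside sampling error.

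Most of this stands, and it rules out several stronger readings that a reader might infer:

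- **That 7.2 and 4.15 contradict each other.** They do not, as Step 1 shows.
- **That the very staff who pay incentives choose, knowing the arm, which contacts to count.** No sentence says so. Extraction is assigned to the research assistant, and that person's knowledge of arm is inferred from 7.1.2.
- **That searching is uneven, or that results will favour Arm 1.** Nothing shows this; the direction would be conjecture.
- **That the analytics unit is already set up to run an event query.** Section 7.2 gives it only the conversion of coded files for analysis.

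What does not stand is that low power makes the matter irrelevant. Section 4.17 intends these estimates for planning, and a systematic shift affects the estimate itself, whether or not it is tested.

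**Conclusion.** The point holds as a cheap improvement, not as an error in the plan. The stated method is individual chart review by a team the plan leaves unblinded, and no provision makes classification mechanical or masked. The consequence is a risk of differential ascertainment, mainly in asthma attribution and steroid courses, confined to the secondary event and cost estimates.

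Its size cannot be taken from the documents. Under an assumed 5-10% shortfall in one arm, a null rate ratio would read 0.95-0.90 and the false-positive rate would be 5.6-7.9% instead of 5.0%. These figures rest on the assumed shortfall, the 50% background rate and 40 to 50 children per arm; the event counts in Step 5 also rest on the assumed upper rate of 2.0 per child-year. The sample size and the adherence analysis do not change.

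**What to change.** In 7.2 and 4.11.1, state that in-study CHOP events are identified by applying the 4.15 definitions (visit diagnoses, medication orders, pathway order set) as one fixed rule to all randomized children, keyed by study ID with no arm field. Have unclear cases classified from a listing without arm by someone already masked under 7.1.2, that is, the PI or the statistics team. Analyse caregiver-reported events outside CHOP separately, because this change does not mask them.

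The cost is some query programming, which goes beyond the analytics unit's stated role and would have to be agreed. Events recorded only in free text may be missed. Sample size, visits and participant burden are unchanged.
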